Esophageal self-dilation therapy (ESDT), where the patient learns to pass a polyvinyl dilator orally on a routine basis, has been in practice since at least the 1970s, however, no prospective studies have evaluated the outcomes ESDT. The largest study to date on ESDT retrospectively studied 30 patients¹², and all the published studies on this topic consists of less than 50 patients in total¹²⁻¹⁹. In these retrospective and observational studies, ESDT appears to be effective for RBES, reducing the number of endoscopic dilations from an average of 21.7 to an average of 1¹². However, many questions with regards to ESDT remain unanswered. Firstly, in the absence of any prospective data it is uncertain how effective ESDT is. Moreover, currently patients are offered ESDT when standard therapies fail.

Hypotheses:

Among patients with refractory benign esophageal stricture who were treated endoscopically, we hypothesized the following:

- 1. Compared to an endoscopy as needed approach, esophageal self-dilation therapy decreases the number of endoscopic dilations and prolongs dysphagia free intervals
- 2. Esophageal self-dilation therapy is a safe and well tolerated therapy
- 3. ESDT significantly lowers health cost in managing refractory esophageal stricture

Primary Aims:

1. Assess the clinical efficacy of ESDT for patients with RBES defined as number of endoscopic interventions 6 months following serial dilation

Secondary Aims:

- 1. Length of intervention free interval and dysphagia score
- 2. Evaluate factors which could influence clinical success of ESDT including etiology and location of the stricture
- 3. Assess the safety of ESDT by identifying clinically significant adverse events including perforation, bleeding and pain.
- 4. Assess acceptance of ESDT by measuring the number of patients who accepts the procedure and are able to complete it over the total number of patients offered ESDT
- 5. The cost saving in ESDT compared to the current standard of care (repetitive endoscopic dilation)
- 6. Evaluate long term outcomes of self-dilatation at 3, 6, 9 and 12 months following participation in the 6 month randomized or prospective observational trial

Methods:

Study Design:

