- 2. Patients in the randomized observation group will receive endoscopic dilation as needed with charges to the patients and their health insurance as appropriate since this is the standard of care
- 3. Patients in both groups will receive stipend of \$25 for each questionnaire for the time spent in completing the dysphagia questionnaire during the randomized 6 month study duration
- 4. Patients who participate in the prospective observational study, and who either chose self-dilation or observation will receive stipend of \$25 for each questionnaire for the time spent in completing the dysphagia questionnaire

Patients who agree to the prospective extension study will receive a stipend of \$25 for each of the 4 monthly MDQ phone calls to collect questionnaires.

Statistical Analysis:

Sample Size Estimation:

Based on the current knowledge from our prior experience, the clinical success of ESDT appears to be 80%. The clinical success of repetitive endoscopic dilation is reported in the literature to be 30%. Assuming a 50% improvement in clinical success with ESDT and using 1:1 randomizing, the estimated minimum number of patients needed is 30 patients (15 in each group). Given the extreme paucity of data on self dilation and ambiguity about the potential improvement we intend to recruit 40 patients across the two sites (Rochester and Phoenix). This estimated number will provide at least 80% power of finding a significant difference at a P value of 0.05

Up to 40 patients who chose not to participate in the randomized trial, but who agree to be followed in the prospective observational group will be recruited.

The following table summarizes the key questions and corresponding approaches to be addressed by this study.

Primary Endpoint:

1. Compare the number of endoscopies required in a 6 month interval in patients who achieved at least a 10-12 mm esophageal diameter during serial dilation for RBES and were subsequently treated with ESDT versus standard clinical care.

Secondary Endpoints:

- 1. Determine the length of intervention free interval
- 2. Dysphagia score
- 3. Number of clinically significant adverse events including perforation, bleeding and pain
- 4. Cost of ESDT compared to the current standard of care (repetitive endoscopic dilation)

Definition:

Perforation will be defined as Evidence of air or luminal contents outside the GI tract. Bleeding will be defined as hematemesis and/or melena or hemoglobin drop >2 g/L

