Question	Approach	Statistical Test
Clinical success	Compare the number of	Logistic regression in a
	patients who remained free	univariate and multivariate
	of endoscopic therapy	analysis
	between the two groups	
Time to the next endoscopy	Compare time endoscopic	Cox regression and Kaplan
	therapy. Patients who	Meier
	requires endoscopic dilation	
	will be considered failure	
Adverse events	Compare the number of	Logistic regression in a
	patients who developed	univariate and multivariate
	adverse events between the	analysis
	two groups	
The cost	Compare the cost of	Linear regression
	treatment including	
	endoscopic therapy,	
	hospitalization from	
	complications	
Factors affecting clinical	Investigating factors which	Multivariate logistic regression
success in ESDT	could determine clinical	
	success including age,	
	gender, etiology, length of	
	the stricture and location of	
	the stricture	

References:

- 1. Spechler SJ. American gastroenterological association medical position statement on treatment of patients with dysphagia caused by benign disorders of the distal esophagus. Gastroenterology 1999;117:229-33.
- 3. de Wijkerslooth LR, Vleggaar FP, Siersema PD. Endoscopic management of difficult or recurrent esophageal strictures. Am J Gastroenterol 2011;106:2080-91; quiz 2092.
- 6. Ramage JI, Jr., Rumalla A, Baron TH, et al. A prospective, randomized, double-blind, placebo-controlled trial of endoscopic steroid injection therapy for recalcitrant esophageal peptic strictures. Am J Gastroenterol 2005;100:2419-25.

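### The only planned safety comparison pools pain, which has no criterion, with perforation and bleeding and counts patients rather than events, so pain can drive or mask the result

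*Combined protocol and SAP*

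**What the plan says.** All references are to the combined protocol and SAP.

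- **Hypotheses, item 2:** "Esophageal self-dilation therapy is a safe and well tolerated therapy". No acceptable event rate or margin is attached.
- **Secondary Aims, item 3:** "Assess the safety of ESDT by identifying clinically significant adverse events including perforation, bleeding and pain".
- **Secondary Endpoints, item 3:** "Number of clinically significant adverse events including perforation, bleeding and pain". This is a count of events.
- **Definition:** "Perforation will be defined as Evidence of air or luminal contents outside the GI tract", and "Bleeding will be defined as hematemesis and/or melena or hemoglobin drop >2 g/L". Pain gets no scale, grade, duration or cut-off, and the phrase clinically significant is not explained.
- **Statistical-analysis table, adverse-events row:** the quantity compared is the number of "patients who developed" adverse events in each group. The method begins "Logistic regression in a" and covers a univariate and a multivariate analysis. No row separates events by type or severity. Complications appear elsewhere in the table only as a hospitalization cost.
- **Secondary Aims, item 4:** acceptance of ESDT, measured as patients who accept and complete it over patients offered it.
- **Sample Size Estimation:** 40 randomized patients, 1:1, so 20 per arm. The calculation rests on clinical success only.

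**The concern.** Three kinds of event that differ greatly in consequence enter one yes/no outcome per patient, and the mildest of them has no threshold. This has two effects.

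First, pain can drive the result. If more patients in one arm report pain, that arm looks less safe even when nobody has a perforation or a bleed.

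Second, pain can mask the result. A patient who has already reported pain is already counted, so a later perforation in that patient changes nothing in the comparison. If pain is common in both arms, a real difference in serious events is diluted.

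The endpoint and the analysis also use different units. The endpoint counts events and the table counts patients. Under the endpoint, a perforation after reported pain adds one; under the table row, it adds nothing.

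The arms differ in exposure by design. Under Study Flow and Recruitment, items 5 and 6, ESDT begins at two self-dilations a day, while observation patients are dilated only at relapse. An imbalance in pain is therefore plausible, although the documents do not say how large it would be or in which arm. At stake is the safety half of hypothesis 2, for a treatment that the introduction says has never been evaluated prospectively.

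**Working it through.** **Inputs.** From the documents: 20 per arm, 1:1 allocation and a significance level of 0.05. Assumed, because the documents give no adverse-event rates: every pain and serious-event rate below. Serious means perforation or bleeding. Pain and serious events are taken as independent.

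**The plan's own figure.** It concerns clinical success, 80% v 30%. With pooled variance, two-sided 0.05 and 80% power, the mean proportion is 0.55 and

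n = [1.96·√(2·0.55·0.45) + 0.8416·√(0.8·0.2 + 0.3·0.7)]² / 0.5² = (1.379 + 0.512)² / 0.25 = 14.3, rounded up to 15 per arm.

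This reproduces the stated 15 per group. It carries no information on safety.

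**Step 1: pain drives the result.** Set serious events to zero in both arms, so that the any-event rate equals the pain rate. With X and Y the numbers of affected patients in the two arms, power is the sum of P(X = x)·P(Y = y) over all pairs (x, y) with p ≤ 0.05, where both counts are binomial with n = 20.

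| Pain, ESDT v observation | Chi-square | Fisher |
|---|---|---|
| 50% v 30% | 25% | 16% |
| 50% v 20% | 53% | 41% |
| 50% v 10% | 84% | 74% |

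The planned method is logistic regression. Chi-square and Fisher stand in for its unadjusted form, and the table shows how much the choice of test matters.

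**Step 2: pain masks the result.** Let serious events be 30% v 2%, with the same pain rate q in both arms. The any-event rate is 1 − (1 − s)(1 − q), where s is the serious-event rate. For q = 50% this gives 1 − 0.70·0.50 = 65% and 1 − 0.98·0.50 = 51%.

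| Pain in both arms | Any event, ESDT v observation | Fisher power |
|---|---|---|
| none (serious events alone) | 30.0% v 2.0% | 62% |
| 20% | 44.0% v 21.6% | 23% |
| 30% | 51.0% v 31.4% | 15% |
| 50% | 65.0% v 51.0% | 8% |
| 70% | 79.0% v 70.6% | 5% |

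**Step 3: the direction can reverse.** With serious events 10% v 1% and pain 20% v 40%, the any-event rates are 1 − 0.90·0.80 = 28% and 1 − 0.99·0.60 = 40.6%. ESDT then looks safer with ten times the serious-event rate.

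**Step 4: what separation can deliver.** A separate Fisher test needs at least 5/20 v 0/20 (p = 0.047); 4/20 v 0/20 gives p = 0.106. With 0/20, the exact two-sided 95% upper limit is 1 − 0.025^(1/20) = 16.8%. Separation therefore supports estimation, not a useful test.

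**The case against.** The strongest objection is that masking is inferred from one line of a summary table. Secondary endpoint 3 counts events and names three types, and the Definition section treats two of them separately. Nothing forbids a table by type, and investigators would probably produce one. That is fair as far as it goes: tabulation by type is neither planned nor excluded. But the table row is the only comparison that the plan specifies, and followed as written it pools.

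Four stronger readings are tempting, and the documents do not support them.

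- *The plan has nothing on tolerability.* Secondary Aim 4 measures acceptance and completion. Study Flow and Recruitment, items 8 and 10, identify patients who cannot tolerate self-dilation and count crossover as treatment failure. Aim 4 has no entry in the endpoint list and no table row, but tolerability is addressed.
- *Pain will be frequent under ESDT.* This is an assumption. The endpoint is limited to clinically significant events, even though the term is undefined. The weekly calls in item 11 are not restricted to the ESDT arm, so they do not themselves create unequal ascertainment.
- *The any-event test will usually flag ESDT as unsafe.* The 84% is the top of the range shown. The plan's own 30% success rate for endoscopic dilation implies that about 100% − 30% = 70% of observation patients would need a dilation, so 10% pain in that arm may be low. At 50% v 30% the figure is 25%.
- *Pooling is the reason that safety cannot be tested.* It is one reason. There is no acceptable rate or margin, and 20 per arm is too few for rare events even when the types are separated (Step 4).

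**Conclusion.** The point holds in this form: the one planned safety comparison mixes undefined pain with perforation and bleeding, and counts patients where the endpoint counts events, so its result can be driven or masked by pain. The finding about structure comes directly from the text and needs no assumed rate.

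The size does rest on assumptions. Over the scenarios examined, pain alone makes the comparison significant in 25% to 84% of trials by chi-square (16% to 74% by Fisher). A large serious-event difference of 30% v 2% falls from 62% power to between 23% and 5%. These figures assume 20 evaluable patients per arm, independence of pain and serious events, and unadjusted tests in place of the logistic model.

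A reader might infer that splitting the types would let the trial establish safety. It would not. It would show what 20 per arm can and cannot exclude. The primary endpoint is unaffected. The change is worth making because safety is a named hypothesis, and pain severity not recorded at the time is hard to recover later.

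**What to change.** 1. Replace the adverse-events row with three: perforation, bleeding and pain. Report each by arm, both as patients affected and as number of events, with an exact 95% confidence interval. Use a binomial interval for patients. A Poisson interval for events is only approximate when one patient contributes several.
2. State one criterion for clinically significant pain (scale, cut-off and duration), chosen by the study team before data are seen and applicable in the same way to both arms. A criterion tied to interrupting dilation would not qualify, because it has no clear counterpart in an arm dilated only at relapse.
3. Report pain as tolerability, next to the acceptance and completion measure of Secondary Aim 4.
4. Word the safety conclusion as descriptive and quote the upper confidence limits for perforation and bleeding. State that a non-significant any-event comparison will not be read as evidence of safety.
5. Because crossover is allowed, record the treatment in use when each event occurs, so that counts by assigned arm can be interpreted.

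**Cost.** Some table wording, one definition and a follow-up question on weekly calls that are already planned. The downside is a more cautious safety conclusion, because the intervals are wide with 20 per arm.

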- 5. Patients randomized to ESDT will be taught ESDT immediately following the last endoscopic dilation. ESDT teaching will take over 1-3 training sessions by one of two esophageal physicians and a nurse. Patients will be instructed to start ESDT twice a day. If dysphagia is adequately controlled, and there was no resistance with passing the dilator, patients will be asked to decrease the frequency of ESDT to daily, weekly, and monthly over an average period of 6 months as directed by the esophageal care team.
- 6. Patients randomized to the observation group will undergo repeat endoscopy and dilation as needed if their dysphagia relapse which is the current standard of care. A relapse will be considered if a patient developed solid food dysphagia at least once a week.
- 7. Patients in the observation group who requires 2 endoscopic dilation within 3 months will be offered to cross over to the self dilation group
- 8. Patients in the self dilation group who can not tolerate self dilation but require more treatment will be offered to crossover to the standard clinical care grouph endoscopic dilation as needed after 3 months from the entry point
- 9. At the end of the six months, the standard clinical care group will be offered self-dilation.
- 10. At any point of the study if patients decide to crossover to the other group, this will be allowed but counted as treatment failure
- 11. Close supervision and follow up will be performed via weekly phone calls from a member of the study personnellPatients will be asked to complete the MDQ-30 monthly and at the end of the study.
- 12. Patients who decline participation in the randomized study will be offered both treatments clinically then will be followed prospectively and their data will be collected. These patients will be asked to fill the dysphagia score to assess symptoms regardless of the method of treatment.
- 13. At the conclusion of the 6 months randomized or observational study duration patients will be offered the following:
 - 1. All patients who participated in the randomized or observational study will be offered to continue prospective follow up with phone calls to obtain the MDQ-30 score and

need for endoscopy at 3, 6, 9, and 12 months after conclusion of the initial 6 month duration of the study

Remuneration:

- 1. Patients in the randomized self-dilation group will be provided with the self-dilator free of charge.

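### The bleeding definition lets a hemoglobin fall of just over 2 g/L (0.2 g/dL) count as a bleed on its own; read literally, this can score ordinary test variation as a clinically significant adverse event, so the unit needs checking

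*Combined protocol and SAP*

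**What the plan says.** The only definition of bleeding is in the Definition section, after the secondary endpoints: "Bleeding will be defined as hematemesis and/or melena or hemoglobin drop >2 g/L". No other section gives a hemoglobin threshold or unit, and none states a reference value, a time window or a confirmation rule.

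Bleeding feeds a safety endpoint that carries a qualifier. Secondary Endpoints, item 3, reads "Number of clinically significant adverse events including perforation, bleeding and pain", and Secondary Aims, item 3, uses the same qualifier. The related hypothesis (Hypotheses, item 2) is "Esophageal self-dilation therapy is a safe and well tolerated therapy".

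The Adverse events row of the analysis table counts patients, compares "adverse events between the" two arms by logistic regression, and does not repeat the qualifier.

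No hemoglobin test is scheduled. Under Study Flow and Recruitment, item 11, "follow up will be performed via weekly phone calls from a member of the study" team, and patients "will be asked to complete the MDQ-30 monthly and at the end of the study".

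**The concern.** The final *or* in the definition makes the hemoglobin fall enough without any visible bleeding. A fall of 0.2 g/dL is very small for an event that is meant to be clinically significant. Two blood samples from a person who has not bled can easily differ by that much.

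What this means depends on how the definition and the endpoint label work together, and the text allows two readings.

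1. **Every defined bleed counts.** This is the literal reading of the Adverse events row. A patient who has not bled can then enter the between-group safety comparison as a bleed.
2. **A defined bleed counts only if it is also clinically significant.** This is coherent. The hemoglobin criterion then excludes little, and the significance judgement does all the work.

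At stake is the comparison that bears on the safety hypothesis. The plan says "we intend to recruit 40 patients across the two sites (Rochester and Phoenix"), which at 1:1 is about 20 per arm. One miscoded patient would move an arm's event proportion by 1/20, or 5 percentage points. That is arithmetic on the planned size, not a forecast that miscoding will occur.

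**Working it through.** The threshold is a stated definition. The documents give no inputs from which it could be derived, so there is no figure of the plan's own to reproduce. The check is whether the threshold can separate a bleed from chance.

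**Inputs**
- From the Definition section: a fall of more than 2 g/L, sufficient alone.
- Assumed, not in the documents: true hemoglobin (Hb) of 120, 140 or 160 g/L; test-to-test coefficient of variation (CV) within a person of 1–4%; one earlier and one later test; independent normal errors; no bleeding.

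**Step 1, unit.** 2 g/L ÷ 10 = 0.2 g/dL. Relative size: 2/160 = 1.25%, 2/140 = 1.43%, 2/120 = 1.67%.

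**Step 2, spread of a difference between two tests.** SD = Hb × CV × √2. The smallest case is 120 × 0.01 × 1.414 = 1.70 g/L; the largest is 160 × 0.04 × 1.414 = 9.05 g/L. The 95% limits for a chance change are 1.96 × SD, so ±3.3 g/L in the smallest case and ±17.7 g/L in the largest. A 2 g/L change lies inside these limits throughout.

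**Step 3, chance of meeting the criterion without bleeding.** P(fall > d) = 1 − Φ(d / SD). At d = 2 the extremes are 1 − Φ(2/1.70) = 0.119 and 1 − Φ(2/9.05) = 0.413.

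If results are reported to the nearest 1 g/L, a fall of more than 2 means a fall of at least 3. The chance is then summed exactly over the two rounded normal distributions.

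| CV | Continuous values, Hb 120 / 140 / 160 | Reported to 1 g/L, Hb 120 / 140 / 160 |
|---|---|---|
| 1% | 12% / 16% / 19% | 7% / 11% / 14% |
| 2% | 28% / 31% / 33% | 23% / 26% / 29% |
| 3% | 35% / 37% / 38% | 31% / 34% / 36% |
| 4% | 38% / 40% / 41% | 36% / 38% / 39% |

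**Step 4, the same check at ten times the threshold.** For d = 20 g/L (2 g/dL), the worst case is Hb 160 g/L and CV 4%: 1 − Φ(20/9.05) = 0.0136 with continuous values, and 0.0118 if reported to 1 g/L.

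These are chances per tested patient. The number of patients tested is unknown, so they cannot be turned into an expected number of events.

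**The case against.** The strongest case on the other side has four parts.

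- **The label can act as a filter.** A permissive definition followed by a significance judgement is a workable design, and the analysis table is a summary that may simply shorten the endpoint's name. This stands. A reader might infer that threshold and label conflict on any reading; they do not. The false-bleed problem belongs to the literal reading of the table row. The plan gives no rule for judging significance, but that is a separate gap, and it applies to pain as well.
- **The unit slip is inference.** A reader might infer that g/dL was plainly intended. The documents contain no second figure that shows this, and an error in reading the text from the source file cannot be excluded. This stands too: it is a question to put to the sponsor.
- **The percentages are not estimates for this trial.** All their inputs are assumed, and no hemoglobin tests are planned. A reader might multiply them by 40 and expect about 5 to 16 false bleeds (40 × 0.119 = 4.8; 40 × 0.400 = 16.0, for Hb 120–140 g/L). That requires every patient to have a before-and-after pair, which nothing in the documents supports. Nor do they support a claim that one arm is favored: more testing in one arm could bias the comparison, but how often each arm is tested is not stated.
- **Only one part of a secondary endpoint is involved, with no demonstrable effect on a result.** This limits the weight of the point but does not remove it. Unscheduled testing affects how often the criterion is applied, not what it says, and the correction is cheap.

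**Conclusion.** The point holds in a limited form. As written, a hemoglobin fall of just over 0.2 g/dL is a bleed on its own. If every defined bleed counts, about 7–41% of tested patients who have not bled would meet the criterion on one repeat test, against at most about 1.4% for a 20 g/L fall. The range rests on an assumed hemoglobin of 120–160 g/L and CV of 1–4%, but 2 g/L is within chance variation at every combination tried. If clinical significance is applied as a separate filter, the definition is coherent and the hemoglobin criterion is merely weak.

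Confidence is high in the literal text and the arithmetic. It does not extend to the explanation that the unit was mistyped.

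One component of a secondary safety endpoint is affected, and only in patients who happen to be tested. The primary endpoint and sample size are unaffected. The correction should be made, but the point does not call the trial's main conclusion into question.

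**What to change.** 1. Check the unit against the source document and correct the outcome definition, ideally before adverse events are coded.
2. If g/dL was meant, write >2 g/dL (20 g/L).
3. If g/L was meant, keep the criterion, since it can catch bleeds without hematemesis or melena. State both in the Definition section and in the Adverse events row that a hemoglobin-only event counts only if it is also judged clinically significant.
4. Use only hemoglobin values already available from clinical care as the reference.
5. Date the change. If any bleed has already been coded on hemoglobin alone, re-check it without knowledge of treatment arm, because recoding a between-group safety outcome in an open comparison carries its own risk of bias.

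The cost is a short edit and a brief re-check, with no new visits or tests. The downside is that patients without an earlier hemoglobin value cannot be assessed on this criterion, so ascertainment will remain uneven.

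### Adverse events are to be compared by logistic regression with about 20 patients per arm and no sparse-event method; if one arm has no events, the odds ratio is not estimable and the conclusion depends on an unstated choice of p-value

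*Combined protocol and SAP*

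**What the plan says.** In the table of questions, approaches and statistical tests, the Adverse events row compares the number of "patients who developed" adverse events between the two groups. Its test column reads "Logistic regression in a" univariate and multivariate analysis. The same words open the test entry of the Clinical success row; the point here concerns the Adverse events row only.

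The endpoint is item 3 under Secondary Endpoints: "Number of clinically significant adverse events including perforation, bleeding and pain". It serves Hypothesis 2 (that self-dilation is safe and well tolerated) and Secondary Aim 3.

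On size, Sample Size Estimation says "we intend to recruit 40 patients across the two sites (Rochester and Phoenix"), "using 1:1 randomizing", which makes 20 per arm. The stated minimum is 15 per arm.

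The plan does not say whether inference is by Wald, likelihood-ratio or score test. It names no exact or penalised method and gives no expected adverse-event rate.

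**The concern.** With 20 patients per arm and possibly uncommon events, one arm may have none. A logistic model with arm as the only covariate then has no finite odds ratio: the estimate drifts upward until the fitting routine stops, and the standard error grows with it. The Wald p-value printed beside the coefficient in standard output moves towards 1 however many events the other arm has. This differs from having too many covariates for the number of events, because the arm-only model is already affected. The multivariate model in the same row adds further risk of separation.

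At stake is the plan's only formal between-arm comparison of safety. Events in one arm and none in the other, if they fall in the self-dilation arm, are the pattern that most contradicts Hypothesis 2. In that pattern the planned effect measure does not exist, and the p-value depends on a choice the plan leaves open.

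**Working it through.** **Arm size.** The only related figure in the plan is the sample size for clinical success: 80% versus 30%, 1:1, 5% level, 80% power. Taking the test as two-sided, with pooled variance and mean proportion 0.55:

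n = [1.960·√(2·0.55·0.45) + 0.842·√(0.8·0.2 + 0.3·0.7)]² / 0.5² = (1.379 + 0.512)² / 0.25 ≈ 14.3, so 15 per arm and 30 in total.

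The plan's figure is reproduced. It bears on adverse events only by fixing the scale; below I use the intended 20 per arm.

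**Chance of an empty arm.** This is (1 − risk)^20. The risks are assumptions:

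| Assumed risk | Chance of 0/20 |
|---|---|
| 2% | 0.98^20 = 67% |
| 5% | 0.95^20 = 36% |
| 10% | 0.90^20 = 12% |
| 20% | 0.80^20 = 1% |

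**10/20 versus 0/20.**
- Maximum likelihood: no finite log odds ratio. Fitted values ran to 17–24 depending on the routine, with standard errors from about 1,100 to 17,800. Wald p = 0.988 to 0.999.
- Likelihood ratio, same model: log-likelihood with separate arms 20·ln 0.5 = −13.86; pooled 10·ln 0.25 + 30·ln 0.75 = −22.49; statistic 2·8.63 = 17.26; p = 0.00003.
- Fisher: 2·C(20,10)/C(40,10) = 0.0004.
- Firth with profile penalised likelihood: log odds ratio 3.71, p = 0.00014. The Wald p from the Firth fit is 0.015, so the inference method matters there too.

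**3/20 versus 0/20.**
- Wald: p about 1 (0.94 to 0.999 across routines).
- Likelihood ratio: 2·[(3·ln 0.15 + 17·ln 0.85) − (3·ln 0.075 + 37·ln 0.925)] = 2·(−8.454 + 10.655) = 4.40; p = 0.036.
- Fisher: 2·C(20,3)/C(40,3) = 2·1,140/9,880 = 0.23.

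**One event in the second arm, 10/20 versus 1/20.** Log odds ratio ln 19 = 2.94; SE = √(1/10 + 1/10 + 1 + 1/19) = 1.12; Wald p = 0.0085. The near-1 Wald p-value is specific to the zero cell.

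**Operating characteristics.** These come from enumerating all 21 × 21 outcomes at 20 per arm, two-sided 5%, with Wald counted as non-significant when a cell is zero:

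| Assumed risks | Wald | Fisher |
|---|---|---|
| 2% vs 30% | 12% | 62% |
| 5% vs 40% | 42% | 72% |
| 10% vs 40% | 46% | 49% |
| 20% vs 50% | 48% | 41% |
| 2% vs 10% | 0.1% | 3% |
| 5% vs 15% | 1% | 7% |

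With a common 10% risk in both arms, the type I error is about 8.5% for the likelihood-ratio test, 1.2% for Fisher and 0.15% for Wald.

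**What an empty arm shows.** The exact two-sided 95% upper limit for 0/20 is 1 − 0.025^(1/20) = 16.8%. Even no events at all would leave a substantial risk possible.

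**The case against.** A reader might infer that a signal as strong as 10/20 versus 0/20 would be reported with p about 1. The documents do not support that. They name logistic regression but not the Wald test. The likelihood-ratio and score tests of the same model detect this signal clearly (p = 0.00003 and 0.00026), and exact or Firth logistic regression would also fit the wording. What fails is the odds-ratio estimate and Wald inference, not every test from the model.

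A reader might also infer that an empty arm is the usual case. That is not shown. The endpoint includes pain, and control patients have repeat endoscopic dilation at relapse. The plan puts success of that approach at 30%, so about 70% would need further endoscopic therapy. The composite may therefore be common enough that neither arm is empty. On the other hand, only clinically significant events count, the Definition section covers perforation and bleeding but not pain, and no rate is given, so the matter cannot be settled either way.

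Nor is Fisher uniformly better: at a 10% risk in the lower arm the gap is small, at 20% Wald has the higher power, and when events are uncommon in both arms both tests have almost none. An infinite or absurd odds ratio would also be visible beside the raw counts, and nothing in the plan says that a non-significant result will be taken as evidence of safety.

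These points narrow the concern but do not remove it. The odds ratio remains inestimable with a zero cell whichever test is used. The likelihood-ratio test is not a safe default, since it is liberal at a common 10% risk. Leaving the choice open allows it to be made after the counts are known.

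**Conclusion.** The point holds in limited form. The plan names a model whose effect measure does not exist if one arm has no events, and does not say how the p-value will be obtained. In that case the safety conclusion can turn on the choice: at 3/20 versus 0/20 only the likelihood-ratio test is below 0.05, while at 10/20 versus 0/20 only Wald misses the signal. The Wald power loss is severe when one arm's risk is near 2% to 5% and the other's is high, and it is small or reversed at 10% to 20%.

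This rests on 20 per arm, two-sided 5% tests and assumed event risks, since the documents give none. It concerns a secondary endpoint and can be corrected in the text, so it should be fixed but does not threaten the trial's main comparison.

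**What to change.** In the Adverse events row, replace the test with an exact comparison of the proportion of patients with an event, naming Fisher's or Boschloo's test before any outcome data are seen. Report the risk difference with its exact 95% confidence interval, and each arm's proportion with its exact interval. If a model is kept, use Firth-penalised logistic regression with arm as the only covariate and profile-likelihood inference. State that a non-significant difference will not be read as showing safety, and that the intervals carry the interpretation.

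The cost is wording only, with no extra patients or data. Fisher is conservative and has somewhat less power than Wald when events are common (41% versus 48% at assumed risks of 20% versus 50%). The multivariable odds ratio for adverse events is dropped.
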